#### **8.5.4 Statistical issues**

##### **8.5.4.1 Adjustment for covariates**

In the analysis of efficacy, in order to consider the effect of the measurement value of the first day of the treatment period on the change of each measurement in the group comparison, the analysis by the MMRM model should be conducted using the measurement value of the first day of the treatment period as a covariate in the general analysis including the analysis of the primary endpoint. A sensitivity analysis of the primary endpoint should be similarly conducted using ANCOVA with the measurement value of the first day of the treatment period as a covariate.

##### **8.5.4.2 Use of the “Subpopulation for efficacy evaluation” of patients**

The primary analysis for the primary endpoint should also be performed similarly for the PPS to examine the robustness of the results.

##### **8.5.4.3 Handling of dropout or missing data**

Provided in "7. Data handling."

##### **8.5.4.4 Interim analysis and data monitoring**

This statistical analysis plan regulates statistical analysis plan of fixed data in the treatment period 1. In the final fixed data, a separate statistical analysis plan should be prepared to perform statistical analysis.

##### **8.5.4.5 Multicenter trial**

For FAS, the following analysis should be conducted for each following endpoint for each facilities. Descriptive statistics of Hb values should be calculated at Week 24 of the treatment period (imputed by the LOCF method) for each treatment group.

Descriptive statistics of mean dose of the study drug should be calculated for Week 20 to Week 24 of the treatment period for each treatment group.

##### **8.5.4.6 Subgroup analyses**

For the FAS, the following analyses should be performed for subgroups based on stratification factors (Table 8.5.4.6.1) for each of the following endpoints.

- (1) Hb value at Week 24 of the treatment period

LSMean, standard error, and 2-sided 95% CI should be calculated for each treatment group using the MMRM model (with compound symmetry [CS] for within-subject variance-covariance matrix). The point estimate, its standard errors, 2-sided 95% CI, and p-value should be calculated for the between-group difference (MT-6548 – darbepoetin) of LSMean.

(2) Study drug mean dose at Week 20 to Week 24 of the treatment period

Descriptive statistics should be calculated for each treatment group.

(3) Target Hb achievement rate at Week 24 of the treatment period

The number, proportion, and 95% CI (Clopper-Pearson [Exact] method) for the proportion of subjects with Hb values within the target range (10.0 g/dL to <12.0 g/dL) should be provided for each treatment group. The estimate, its 95% CI (exact method), and p-value (Fisher's exact test) for group difference (MT-6548 – darbepoetin) should be calculated.

Table 8.5.4.6.1 Subgroup analyses of efficacy

Endpoints	Stratification factor	Stratified category
1. Hb at Week 24 of the treatment period	Sex	Male, Female
2. Study drug mean dose at Week 20 to Week 24 of the treatment period	Age at time of consent (years)	<65, ≥65 <75, ≥75
3. Target Hb achievement rate at Week 24 of the treatment period	Dry weight (kg) on the first day of the treatment period	<60, ≥60
	Body mass index (kg/m  ) on the first day of the treatment period	<25, ≥25
	Underlying cause of CKD	Diabetes, hypertension, autoimmune/glomerulonephritis/vasculitis, interstitial nephritis/pyelonephritis, cystic/hereditary/congenital disease, neoplasm/tumor
	Duration of nephrogenic anemia (years)	<1, ≥1 to <5, ≥5
	Complication	hypertension, diabetes, dyslipidemia
	Hb value (g/dL) on the first day of the treatment period	<10, ≥10 to <11, ≥11
	Liver function test (U/L) on the first day of the treatment period	AST and ALT both not more than the upper limit of normal, either above the upper limit of normal and both ≤2 times the upper limit of normal, either >2 times the upper limit of normal
	CRP (mg/dL) on the first day of the treatment period	<0.31, ≥0.31
	Ferritin (ng/mL) on the first day of the treatment period	Divide the number of subjects into three categories based on the tertile
	TSAT (%) on the first day of the treatment period	Divide the number of subjects into three categories based on the tertile

	Smoking status	3 categories: never smoked, ex-smoker, current smoker
	Administration of oral iron supplement on the first day of the treatment period	Yes or No
	Treatment with oral iron supplement at Week 24 of the treatment period	Yes or No
	Iron-containing phosphate binders on the first day of the treatment period	Yes or No
	Iron-containing phosphate binders at Week 24 of the treatment period	Yes or No
	Previous ESA formulation	Epoetin alfa or epoetin beta, darbepoetin alfa, epoetin beta pegol, other
	Dosage of epoetin alfa, epoetin beta, or epoetin kappa	Divide the number of subjects into three categories based on the tertile
	Dosage of darbepoetin alfa	Divide the number of subjects into three categories based on the tertile
	Dosage of epoetin beta pegol	Divide the number of subjects into three categories based on the tertile
	CYP2B6 inducer combination*	Yes or No

\* List of CYP2B6 inducers obtained from the Metabolism and Transport Drug Interaction Database (DIDB®).

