### 8.7.3 Subgroup analyses

The following analyses should be conducted for subpopulations based on the stratification factor for each endpoint in the below (Table 8.7.3.1) in the FAS.

(1) Hb value at Week 24 of the treatment period

LSMean, standard error, and 2-sided 95% CI should be calculated for each treatment group using the MMRM (with compound symmetry [CS] for a covariance matrix within subject variance). The point estimate of the between-group difference (MT-6548 – darbepoetin) of LSMean, its standard errors, 2-sided 95% CI, and p-value should be calculated.

(2) Study drug mean dose at Week 20 to Week 24 of the treatment period

Descriptive statistics should be calculated for each treatment group.

(3) Target Hb value achievement rate at Week 24 of the treatment period

The number, proportion, and 95% CI (Clopper-Pearson [Exact]) method for the proportion of subjects with Hb values within the target range (10.0 g/dL to <12.0 g/dL) should be provided for each treatment group. The estimate, its 95% CI (exact method), and p-value (Fisher's exact test) for group difference (MT-6548 – darbepoetin) should be calculated.

Table 8.7.3.1 Subgroup analyses of efficacy

Endpoints	Stratification factor	Stratified category
1. Hb value at Week 24 of the treatment period	Treatment with oral iron supplement at Week 24 of the treatment period	Yes or No
2. Study drug mean dose at Week 20 to Week 24 of the treatment period 3. Target Hb value achievement rate at Week 24 of the treatment period	Iron-containing phosphate binders at Week 24 of the treatment period	Yes or No

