## 2.4 Rationale for sample size

A total of 300 subjects (150 each for the MT-6548 and darbepoetin groups) should be enrolled in the treatment period.

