### [Rationale]

For the primary efficacy endpoint of mean Hb values at treatment period Weeks 20 and 24, the mean Hb value in the darbepoetin group is assumed to be 11.0 g/dL, the difference between the MT-6548 and darbepoetin groups is assumed to be 0 g/dL, and the standard deviation for both is assumed to be 1.73 g/dL. The non-inferiority margin is set at -0.75 g/dL. Calculation of statistical power from these assumptions shows that a sample size of 150 subjects in each group would ensure greater than 95% probability that the mean of mean Hb values in the MT-6548 group and their 95% CI would fall within the target Hb range (10.0–12.0 g/dL) and non-inferiority could be established.

The assumed standard deviation was set at 1.73 g/dL based on the upper limit of the two-sided 95% confidence interval of the standard deviation in the MT-6548 300 mg group at Week 6 in study CI-0022.

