### 8.1 Basic matters

#### 8.1.1 Level of significance and confidence coefficient

When implementing tests, level of significance should be set at 2-sided 5%. Confidence interval will be 2-sided with a confidence coefficient of 95%.

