#### 8.5.4.8 A study with active control intended to demonstrate equivalence

This is a non-inferiority study with an active control.

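### The subgroup p-values are computed within each level and no treatment-by-subgroup test is planned, so they do not test whether the effect differs between levels

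*SAP*

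**What the plan says.** Phase 1 SAP 8.5.4.6 applies three analyses to every level of the factors in Table 8.5.4.6.1. Two of them produce p-values.

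- **Hb at Week 24 (item 1).** An MMRM gives least squares means by group. For the difference, the plan asks for the estimate, its standard error and "2-sided 95% CI, and p-value should be calculated for the between-group difference".
- **Target Hb achievement at Week 24 (item 3).** The difference in proportions is given with an exact 95% CI and a Fisher's exact p-value.

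Final SAP 8.5.4.5 repeats both at Week 52. Final SAP 8.7.3 repeats both at Week 24 for two factors, oral iron and iron-containing phosphate binders at Week 24. For Hb it asks for the estimate and adds: "its standard errors, 2-sided 95% CI, and p-value should be calculated".

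The MMRM in Phase 1 SAP 8.5.1 and final SAP 8.5.1 contains one interaction, time point by treatment. No subgroup term appears in either SAP. The -0.75 g/dL margin is applied only to the whole-trial primary analysis.

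Phase 1 SAP 8.5.4.8 states: "This is a non-inferiority study with an active control". Phase 1 SAP 8.5.4.7 calls the secondary and other endpoints exploratory and waives multiplicity adjustment between endpoints and time points, but does not mention subgroups. The final SAP's multiplicity section (8.5.4.6) carries no exploratory label. The errata to the Phase 1 SAP remove the whole-trial Fisher p-value for target achievement as unnecessary and leave the subgroup ones in place.

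**The concern.** The natural question for a subgroup table is whether the treatment effect differs between the levels of a factor. A p-value computed inside one level cannot answer it. It tests that level's own difference, and its result depends on the size of the level as much as on the effect there. When the effect is the same everywhere, chance and unequal precision will often leave one level below 0.05 and another above it.

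A reader of these tables could take that contrast as evidence that MT-6548 performs differently by sex, age, previous ESA or another factor, when nothing in the analysis has tested it. With many factors tabulated and no other subgroup test offered, the risk of that misreading is material, though it concerns secondary tables only.

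**Working it through.** **Inputs from the documents**
- Sample size: 300 in total, 150 per group (SAP 2.4).
- "the standard deviation for both is assumed to be 1.73 g/dL" (SAP 2.4, Rationale).
- "the difference between the MT-6548 and darbepoetin groups is assumed to be 0 g/dL" (same place).
- "The non-inferiority margin is set at -0.75 g/dL" (same place).
- Two-sided 5% level (SAP 8.1.1).

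**Assumptions**
- Subgroup sizes are not given. I take two equal levels, 75 per arm each.
- The planning SD is for the mean of Weeks 20 and 24. I apply it to Week 24. An SD of 1.2 g/dL is also shown as an assumed lower value.
- The null of the Hb p-value is not written out. I take it as zero difference, since no margin-shifted null is given. Fisher's test has a null of equal proportions by construction.
- The two levels are treated as independent, with normal theory and no gain from the baseline covariate.

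**The plan's own figure.** The standard error with 150 per arm is 1.73 × √(2/150) = 0.200. Power for non-inferiority at a true difference of 0 is Φ(0.75/0.200 − 1.96) = Φ(1.79) = 0.964. Adding the target-range condition by simulation gives 0.963. This agrees with the stated figure of more than 95%.

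**Count of planned p-values.** Table 8.5.4.6.1 has 22 rows. Listed categories, row by row, with age counted as 4 and each of the three complications once:

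2+4+2+2+6+3+3+3+3+2+3+3+3+2+2+2+2+4+3+3+3+2 = 62

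Each listed category would have one Hb and one Fisher p-value if it can be estimated. If all 62 could be estimated and every true difference were 0, the expected number of Hb p-values below 0.05 is 62 × 0.05 = 3.1.

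**Discordant levels under a uniform effect.** Within one level, SE = 1.73 × √(2/75) = 0.2825. Let p be the chance that one level is significant: p = Φ(−1.96 + |d|/SE) + Φ(−1.96 − |d|/SE). The chance that exactly one of two levels is significant is 2p(1−p).

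| Uniform difference d (g/dL) | d/SE | p | Exactly one significant, SD 1.73 | Same, SD 1.2 (assumed) | Interaction test |
|---|---|---|---|---|---|
| 0 | 0 | 0.050 | 9.5% | 9.5% | 5% |
| -0.2 | -0.71 | 0.109 | 19% | 29% | 5% |
| -0.3 | -1.06 | 0.186 | 30% | 45% | 5% |

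A difference of -0.3 g/dL is well inside the margin.

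**Power cost of an interaction test.** Suppose the deficit is -0.75 g/dL in one of the two levels and 0 in the other, with SD 1.73.
- Within-level test: 0.75/0.2825 = 2.65, power Φ(0.69) = 76%.
- Interaction test: SE = 0.2825 × √2 = 0.3995; 0.75/0.3995 = 1.88, power 47%.

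**Precision of the planned intervals.** At SD 1.73 the t-based 95% CI half-width is 0.56 g/dL at 75 per arm, 0.69 at 50 and 0.98 at 25.

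**The case against.** A reader might infer that these analyses would conceal a margin-sized deficit in a small subgroup. The documents do not support that reading. The same sentences that ask for the p-value also ask for the 95% CI of the difference. Read against -0.75 g/dL, that interval addresses non-inferiority in the level directly: if the true deficit is exactly -0.75, the lower limit stays at or above the margin in only about 2.5% of trials. In small levels the interval will be wide, and its width makes that plain.

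An interaction test would also be worse at finding a deficit confined to one level, at 47% against 76% in the case above. This stands, and it is the main cost of the change.

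The harm is also conditional. The SAPs do not say how the p-values will be read, and Phase 1 SAP 8.5.4.7 gives an exploratory standing to the endpoints involved. So the tables could mislead, but it cannot be said that they would.

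The count of 62 is of listed categories, not of p-values that will exist. Some categories may be sparse or empty: other previous ESA (inclusion criterion 4 names the permitted agents), AST or ALT above twice the upper limit (2.5 times or more is excluded at screening), and neoplasm as the cause of CKD (malignancy is largely excluded). The higher discordance figures need a true difference other than the planned 0, and the SD 1.2 column is an assumption.

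None of this supplies a test of whether the effect differs between levels, so the core of the point remains.

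**Conclusion.** The point holds in a limited form. Both SAPs plan within-level p-values and no treatment-by-subgroup test, so the p-values do not test heterogeneity of effect. At the planning SD and two equal levels of 75 per arm, a uniform effect produces a one-significant, one-not contrast in about 9.5% of trials at a difference of 0 and in 19% to 30% at -0.2 to -0.3 g/dL. An interaction test is held at 5%. These figures rest on assumed level sizes, on the planning SD carried over to Week 24, and on a zero null for the Hb p-value.

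The fault lies in the p-values, not in the whole subgroup output, because the planned intervals already allow comparison with the margin. A reader might go further and infer that the trial's non-inferiority conclusion is in doubt. It is not: that decision rests on the whole-trial MMRM in Phase 1 SAP 8.5.1, which these tables do not touch. This is an inexpensive improvement to exploratory analyses.

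**What to change.** Amend Phase 1 SAP 8.5.4.6(1),(3) and final SAP 8.5.4.5(1),(3) and 8.7.3(1),(3) as follows.

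1. **Baseline factors.** Replace the within-level p-values with one interaction p-value per factor, from a model on all FAS subjects. Treat each age cut-point separately and each complication as yes/no.
   - Hb: MMRM with subgroup and its interactions with treatment and visit.
   - Target achievement: logistic model with the treatment-by-subgroup interaction, using an exact or penalised method, or pooled levels, where data are sparse. Note that this tests uniformity of the odds ratio, while the planned estimates are differences in proportions.
   - Previous-ESA dose tertiles can only be modelled among users of that agent. The CYP2B6 factor needs a stated time of assessment before it can count as baseline.
2. **Post-randomisation factors.** For oral iron and iron-containing binders at Week 24 or 52, including all of 8.7.3, drop the p-values and present estimates and intervals descriptively. An interaction with a variable measured after randomisation is not a clean test of effect modification.
3. **Keep** the planned estimates and 95% CIs. Show the Hb results in a forest plot with a line at -0.75 g/dL, and label all of it exploratory in both SAPs.
4. **State the limitation.** Interaction tests have low power here, so a non-significant interaction is not evidence of a uniform effect. The intervals should carry the interpretation.

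For the Phase 1 table this leaves 22 + 1 (second age cut-point) + 2 (complications split in three) − 2 (Week 24 factors) = 23 interaction p-values per endpoint. For Hb, 23 × 0.05, or about 1.2, would be significant by chance under any uniform effect. The cost is SAP wording and modest programming, with no new data.

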8.5.2 Restricted concomitant medications and therapies

(1) Iron supplements

From the first day of the screening period to completion of blood sampling for haematology tests on the final day of the treatment period, administer iron supplements to maintain serum ferritin values of ≥ 100 ng/mL or TSAT of $\geq 20\%$. Iron supplements may be omitted for subjects who respond poorly to them, such as those with an allergy or those with adverse drug reaction (ADRs) to iron (vomiting, etc.).

Investigators/subinvestigators will determine iron supplement dosage and administration route.

Important: Oral iron supplements may impair MT-6548 bioavailability, so oral iron supplements must not be taken at the same time as MT-6548 Tablet. Subjects taking oral iron supplements will be instructed not to take any within 2 hours before or after taking MT-6548 Tablet.

(2) Iron-containing phosphate binders (ferric citrate hydrate, sucroferric oxyhydroxide)

New use of iron-containing phosphate binders is fundamentally prohibited from the first day of the screening period to completion of blood sampling for haematology tests on the final day of the treatment period. If iron-containing phosphate binders are used by a subject

on the first day of the screening period, then the same dosage of the same type should fundamentally be continued from the first day of the screening period to completion of blood sampling for haematology tests on the final day of the treatment period. If investigators/subinvestigators determine that a dosage increase is required for iron-containing phosphate binders, then additional treatment will be performed with hyperphosphatemia drugs containing no iron, or treatment switched to hyperphosphatemia drugs containing no iron. Dosage of iron-containing phosphate binders may also be reduced if determined necessary according to the subject's condition.

Important: As with oral iron supplements, iron-containing phosphate binders may impair MT-6548 bioavailability, so iron-containing phosphate binders must not be taken at the same time as MT-6548 Tablet. Subjects taking iron-containing phosphate binders will be instructed not to take any within 2 hours before or after taking MT-6548 Tablet.

(3) Hemodialysis

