	TSAT (%) on the first day of the treatment period	Divide the number of subjects into three categories based on the tertile
	Smoking status	3 categories: never smoked, ex-smoker, current smoker

	Administration of oral iron supplement on the first day of the treatment period	Yes or No
	Treatment with oral iron supplement at Week 52 of the treatment period	Yes or No
	Iron-containing phosphate binders on the first day of the treatment period	Yes or No
	Iron-containing phosphate binders at Week 52 of the treatment period	Yes or No
	Previous ESA formulation	Epoetin alfa or epoetin beta, darbepoetin alfa, epoetin beta pegol, other
	Dosage of epoetin alfa, epoetin beta, or epoetin kappa	Divide the number of subjects into three categories based on the tertile
	Dosage of darbepoetin alfa	Divide the number of subjects into three categories based on the tertile
	Dosage of epoetin beta pegol	Divide the number of subjects into three categories based on the tertile
	CYP2B6 substrate*	Yes or No

\* List of CYP2B6 substrates obtained from the Metabolism and Transport Drug Interaction Database (DIDB®).

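### Between-arm Hb contrasts and p-values in subgroups defined by oral iron (and, less so, iron-containing binder) use at Week 24 or 52 are open to bias of unknown size and direction

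*SAP*

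**What the plan says.** **Contrasts.** Phase 1 SAP 8.5.4.6 asks, in every efficacy subgroup, for MMRM least-squares means of Week 24 Hb and a between-arm comparison: "The point estimate, its standard errors, 2-sided 95% CI, and p-value should be calculated for the between-group difference". It also asks for the between-arm difference in target-Hb achievement, with an exact interval and a Fisher p-value. Final SAP 8.5.4.5 has the same at Week 52, and final SAP 8.7.3 repeats both contrasts at Week 24.

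**Factors.**

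- Phase 1 SAP Table 8.5.4.6.1 includes "Treatment with oral iron supplement at Week 24 of the treatment period" and the matching binder factor.
- Final SAP Table 8.5.4.5.1 includes "Treatment with oral iron supplement at Week 52 of the treatment period" and "Iron-containing phosphate binders at Week 52 of the treatment period".
- Final SAP Table 8.7.3.1 contains only two factors: oral iron at Week 24 and "Iron-containing phosphate binders at Week 24 of the treatment period".

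The two main tables also carry first-day versions of both factors, such as "Administration of oral iron supplement on the first day of the treatment period". The errata to the Phase 1 SAP change Table 8.5.4.6.1 only in its CYP2B6 row, so the iron and binder rows stand.

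**What drives iron and binder use.** Protocol 8.5.2 tells sites to "administer iron supplements to maintain serum ferritin values of" at least 100 ng/mL, or TSAT of at least 20%, and leaves dose and route to the investigator. For iron-containing binders, new use is prohibited in principle and existing use is to continue unchanged. Reduction, or a switch to an iron-free drug, is allowed.

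**The concern.** A between-arm comparison inside a subgroup is protected by randomisation only if treatment could not have influenced who is in the subgroup. A first-day factor meets that condition; oral iron use at Week 24 or 52 does not. Whether a subject is on oral iron then depends partly on ferritin and TSAT during treatment. The SAPs themselves compare iron dose, iron use, ferritin, TSAT and hepcidin between arms (Phase 1 SAP 8.5.3 (5)–(8); final SAP 8.5.2 (5)–(8)), so the plan already treats iron use as something treatment may alter.

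If it does, users on MT-6548 and users on darbepoetin are differently selected patients, and so are non-users. A difference in Hb can then appear in both subgroups when the drugs have the same effect on Hb. Protocol 8.5.2 warns that oral iron and iron-containing binders may reduce MT-6548 bioavailability, so readers are likely to look at these rows. Neither SAP attaches a caveat to them.

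**Working it through.** **Design figure, for reference.** The documents give no figure for these subgroups. Their one design figure is a probability above 95% with 150 per arm, SD 1.73 g/dL, margin −0.75 g/dL and true difference 0 (SAP 2.4).

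- SE = 1.73 × √(2/150) = 0.200.
- 0.75/0.200 = 3.754, and 3.754 − 1.960 = 1.794. Φ(1.794) = 96.4%.
- The target-range condition on the MT-6548 mean is met with probability above 99.99%, so the joint figure is also 96.4%. The plan's statement reproduces, and nothing below alters it.

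**How bias arises.** Let need for iron be a standard normal variable with correlation −c to Hb, and let a fraction p of an arm be users, those with need above z = Φ⁻¹(1 − p). With Hb SD σ and no treatment effect on Hb:

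- mean Hb among users = overall mean − σ·c·φ(z)/p
- mean Hb among non-users = overall mean + σ·c·φ(z)/(1 − p)

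If p differs by arm (p₁ on MT-6548, p₀ on darbepoetin), the spurious MT-6548 minus darbepoetin difference is

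- users: σ·c·[φ(z₀)/p₀ − φ(z₁)/p₁]
- non-users: σ·c·[φ(z₁)/(1 − p₁) − φ(z₀)/(1 − p₀)]

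Both are zero if p₁ = p₀ or c = 0. Both take the same sign, and the sign reverses if p₁ < p₀ or if c is negative.

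**Illustration A (assumed inputs except the SD).** σ = 1.73 from the SAP; use 30% on darbepoetin and 20–50% on MT-6548; a latent factor correlated 0.2 or 0.4 with Hb and −0.7 with need, so c = 0.14 or 0.28. The documents give no iron-use rates by arm. The φ(z)/p values are 1.400, 1.159, 0.966 and 0.798 at p = 0.2, 0.3, 0.4 and 0.5. The φ(z)/(1 − p) values are 0.350, 0.497, 0.644 and 0.798.

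| Use, darbepoetin vs MT-6548 | Users (g/dL) | Non-users (g/dL) |
|---|---|---|
| 30% vs 30% | 0 | 0 |
| 30% vs 40% | 0.05 to 0.09 | 0.04 to 0.07 |
| 30% vs 50% | 0.09 to 0.17 | 0.07 to 0.15 |
| 30% vs 20% | −0.06 to −0.12 | −0.04 to −0.07 |

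For example, users at 30% vs 50% with c = 0.28: 1.73 × 0.28 × (1.159 − 0.798) = 0.175. A simulation with 2 million subjects per scenario gave 0.03 to 0.18 g/dL in absolute size, with the all-subject difference about 0 throughout.

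**Illustration B (extreme, all inputs assumed).** σ = 1.2; correlation of iron status with Hb 0.2–0.4; MT-6548 shifts iron status by 0.5–1.0 SD; users are those below a cut that gives 50% use on darbepoetin. Use on MT-6548 is then Φ(0.5) = 69% to Φ(1.0) = 84%. Users: 0.07 to 0.24 g/dL. Non-users: 0.08 to 0.35 g/dL. The top figure is 1.2 × 0.4 × (1.525 − 0.798) = 0.35.

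**Effect on the p-value in A.** With 150 per arm, non-users at 30% vs 50% number 105 and 75, so SE = 1.73 × √(1/105 + 1/75) = 0.262. A bias of 0.146 is 0.56 SE, and the false-positive rate is Φ(0.56 − 1.96) + Φ(−0.56 − 1.96), about 9% against a nominal 5%. The other scenarios in A give 5–8%. Baseline adjustment would shrink the SE, so the rate could be somewhat higher for the same bias.

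**The case against.** **Bias is not shown.** It needs both an effect of treatment on oral iron use and a link between Hb and what drives that use. The documents establish neither. A reader might infer that these contrasts are biased as planned; the text supports only that they are open to bias. This stands and sets the wording of the conclusion.

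**Binders differ from iron supplements.** The ferritin/TSAT rule governs supplements. For binders, new starts are prohibited in principle, so Week 24 or 52 status should largely match first-day status and change mostly by stopping. Treating the two factors as equally affected would go too far. This stands, although the allowance for reduction or switching leaves some room for change.

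**Large figures need extreme inputs.** The 0.35 g/dL figure requires 50% versus 84% use. The model also equates iron need with oral use, whereas route is at the investigator's discretion and a subject on intravenous iron alone is not an oral user. This stands: the figures are illustrations, not estimates.

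**Two further inferences lack support.** One is that these rows are meant to test whether iron or binders blunt MT-6548. No section says so, and both SAPs have separate MT-6548-only analyses of continuous users against never-users. The other is that the subgroups contain only subjects still on study. The stated population is the FAS, and neither SAP says how withdrawn subjects are classified. That is a gap, not evidence of selection.

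**Standing of the analyses.** Phase 1 SAP 8.5.4.7 calls secondary and other endpoint analyses exploratory, and no decision rule rests on these subgroups. This limits the importance, but the label there concerns multiplicity; it does not make the compared groups alike.

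**Conclusion.** The point holds in limited form. In three tables, between-arm Hb differences and p-values, and Fisher p-values for target-Hb achievement, are planned within subgroups formed by a post-randomisation variable. For oral iron, the protocol's own dosing rule and the SAPs' own between-arm comparisons of iron use make an influence of treatment plausible, so the concern is strong. For binders it is weak. Size and direction cannot be known from the documents: zero under either null condition, about 0.03–0.18 g/dL in absolute size under illustration A, up to 0.35 g/dL under illustration B. The primary MMRM non-inferiority test uses none of these factors and is unaffected, so a reader should not infer any threat to the trial's main conclusion.

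**What to change.** - In Phase 1 SAP Table 8.5.4.6.1 and final SAP Table 8.5.4.5.1, report the Week 24 and Week 52 oral iron and binder factors as by-arm descriptive summaries, without between-arm estimates, intervals or p-values for Hb and target-Hb achievement.
- Base between-arm subgroup statements about iron and binders on the first-day factors already in those two tables.
- Final SAP Table 8.7.3.1 has no first-day factors. Under final SAP 8.7 it exists to check the effect of changed Phase 1 iron data, so removing the contrast would remove what is being checked. Keep the re-tabulation, and label any between-arm contrast there as a data-change check that is not to be read as a treatment effect.

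The cost is a few exploratory contrasts. Sample size, power and the primary analysis do not change.
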